8.4 Safety Analysis

The overall safety profile of study drug will be assessed in terms of the following safety and tolerability endpoints:

- Treatment-emergent adverse events (TEAEs)
- Clinical laboratory values (hematology and serum chemistry)
- Standard 12-lead electrocardiograms
- PEs (clinically significant abnormalities recorded as medical history or adverse events)
- Vital signs (systolic blood pressure, diastolic blood pressure, temperature, pulse rates, and respiratory rate)
- Ophthalmologic examinations

Unless specified otherwise, safety endpoints will be analyzed based on the Safety Set, for the total subjects in the Ivacaftor arm. Only a descriptive analysis of safety will be performed. All safety data will be presented in individual subject data listings. No statistical hypothesis testing will be conducted.

8.4.1 Adverse Events

AEs will be classified as pretreatment AEs, TEAEs, or post-treatment AEs, defined as follows:

Pretreatment AE: any AE that started before the first dose date of study drug in Study 126

TEAE: any AE that worsened (either in severity or seriousness) or that was newly developed at or after the first dose date of study drug through the end of the TE period in the current study.

Post-treatment AE: any AE that worsened (either in severity or seriousness) or that was newly developed beyond the TE period

For AEs with completely missing or partially missing start dates, if there is no clear evidence that the AEs started before or after study treatment, the AEs will be classified as TEAEs.

Details for imputing missing or partial start dates of AEs are described in [Appendix D](#).

AE summary tables will be presented for TEAEs only and will include the following:

- All TEAEs
- TEAEs by strongest relationship
- TEAEs by maximum severity
- TEAEs leading to treatment discontinuation.
- Serious TEAEs
- Related (defined as missing, possibly related, or related) TEAEs
- Serious Related TEAEs

Summaries will be presented by MedDRA System Organ Class and Preferred Term using frequency counts and percentages (i.e., number and percentage of subjects with an event). When summarizing the number and percentage of subjects with an event, subjects with multiple occurrences of the same AE or a continuing AE will be counted once. Only the maximum severity level will be presented in the severity summaries, and the strongest relationship level will be presented in the relationship summaries.

In addition, a listing containing individual subject AE data for TEAEs leading to treatment interruption, TEAEs leading to discontinuation, SAEs, and deaths will be provided separately. All AEs, including pre- and post-treatment AEs, will be presented in an individual subject data listing.

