### 9.1.1.2 Ivacaftor Arm Treatment Period (All Subjects)

Ivacaftor will be administered every 12 hours (q12h) from Day 1 through the morning dose of the Week 96 Visit. At each visit, except the final treatment period visit, the ivacaftor dose for each subject will be reassessed and adjusted if necessary. See Section 9.2.2 for information about ivacaftor doses.

Subjects will be outpatients; study visits will occur as follows:

- For subjects from Study 124 Part B: Day 1 and Weeks 12, 24, 36, 48, 60, 72, 84, and 96.
- For subjects not from Study 124 Part B: Day 1 and Weeks 2, 4, 8, 12, 18, 24, 36, 48, 60, 72, 84, and 96; a telephone contact will occur at Day 3.

Treatment Period assessments are listed in Table 3-1 and Table 3-2 for subjects from Study 124 Part B and in Table 3-3 for subjects not from Study 124 Part B.

#### 9.1.1.2.1 Transition from Study 124 Part B to Day 1 of Study 126

All subjects must sign the ICF before any Study 126-related assessments. Subjects from Study 124 Part B can transition into Study 126 as follows:

- **Same-day Transition:** If the Day 1 Visit is the same day as the Week 24 Visit of Study 124 Part B, the subject will not have to perform any Day 1 assessments that were performed at the Week 24 Visit of Study 124 Part B (Table 3-1).
- **Gap Transition:** If the Day 1 Visit is NOT the same day as the last study visit of Study 124 Part B, all Day 1 assessments will need to be performed (Table 3-2), with the possible exception of the following:
  - Clinical laboratory assessments: Results must be reviewed and eligibility confirmed before dosing on Day 1.
    - If the Day 1 Visit is conducted  $\leq 9$  days after the last study visit of Study 124 Part B, the serum chemistry and hematology assessments performed at the last study visit of Study 124 Part B will not need to be repeated.

- If the Day 1 Visit is conducted >9 days after the last study visit of Study 124 Part B, the serum chemistry and hematology assessments must be repeated on Day 1, and the results must be reviewed and eligibility confirmed before the first dose of study drug.
- OE: If an OE was conducted in Study 124 Part B within 24 weeks of the Day 1 Visit, the Day 1 Visit OE does not need to be repeated. Otherwise, an OE must be conducted within 14 days of the Day 1 Visit. Throughout this study, these subjects should have OEs approximately every 24 weeks ( $\pm$  14 days) from the last OE in Study 124.

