- Clinically significant findings are observed in the slit-lamp examination.

During the course of the study, if ivacaftor is approved and available for the treatment of CF in populations enrolled in this study, subjects may be discontinued at the discretion of the sponsor. If a subject is switching to commercially available ivacaftor, the ETT Visit (Section 9.1.1.5) will be completed before dosing with commercial drug begins, and the Safety Follow-up Visit will not be required.

Alternatively, if local health authorities decline to approve ivacaftor, or if ivacaftor cannot be given to patients within a given age cohort (e.g., an appropriate dose cannot be determined), then subjects of the relevant populations may be discontinued after communication to investigators and IRBs/IECs of the benefits/risks for the relevant subject population. If subjects are discontinued from the study, an ETT Visit should occur as soon as possible after the last dose of study drug and a Safety Follow-up Visit should occur within 4 weeks ( $\pm$  7 days) after the last dose of study drug.

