6.2 Sample Size and Power

The study is not powered to detect a significant treatment effect. The study will enroll approximately 75 subjects.

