8 STATISTICAL ANALYSIS

8.1 General Considerations

The Schedule of Assessments is provided in [Appendix A](#). The precision standards for reporting safety and efficacy variables are provided in an internal Biometrics document that specifies the programming rules including the precision for derived variables.

All individual subject data for subjects who are enrolled in the current study will be presented in individual subject data listings.

As no subjects are enrolled in the Observation Arm, all analyses will be done for subjects from the Ivacaftor Arm only. All analysis will be performed for the Ivacaftor Arm overall, unless otherwise specified.

Continuous variables will be summarized using the following descriptive summary statistics: the number of subjects (n), mean, standard deviation (SD), standard error (SE), median, minimum value (min), and maximum value (max). 95% confidence intervals (CI) may be provided as appropriate.

Categorical variables will be summarized using counts and percentages. 95% CI may be provided as appropriate.

Baseline value is defined in two different ways:

Study 124 baseline: the baseline value for rollover subjects (who participated in Study 124 Part B or Part A/B) is defined as the baseline measurement from Study 124 Part B or Part A/B. That is, the most recent non-missing measurement collected on or before the initial

administration of study drug in Study 124 Part B or Part A/B. Note that this definition is consistent with the definition of baseline in Study 124 and applies to both scheduled and unscheduled measurements; if an unscheduled value is the most recent non-missing measurement, it will be used as baseline.

Study 126 baseline: the baseline value for IVA-naïve subjects (who did not participate in Study 124 Part B or Part A/B) is defined as the most recent non-missing measurement collected on or before the initial administration of study drug in the current study, including both the scheduled and unscheduled measurements.

Change (absolute change) from baseline will be calculated as Postbaseline value – Baseline value.

Relative change from baseline will be calculated and expressed in percentage as 100% × (Postbaseline value – Baseline value)/Baseline value.

Treatment-emergent (TE) Period

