8.3.3.2 Tertiary Analysis

- The following growth parameters will be summarized descriptively as continuous variables by visit (including change from baseline).
 - Weight
 - Length
 - Weight-for-length (expressed as a percentile)
 - BMI
 - Weight-for-age z-score
 - Length-for-age z-score
 - Weight-for-length z-score
 - BMI-for-age z-score

Summary statistics for weight-for-age, length-for-age, and BMI-for-age percentiles may also be provided to aid interpretation of z-scores.

- LCI_{2.5} will be analyzed as a continuous variable using descriptive summary statistics and results (including changes from baseline) presented by visit. In the event that fewer than 3 subjects have these optional assessments available, listings of results may be provided instead of summary statistics.
- Markers of pancreatic inflammation (fecal elastase-1): These parameters will be summarized descriptively as a continuous parameter and results (including changes from baseline) presented by visit. Shifts from baseline will be summarized by visit.
- Marker of intestinal inflammation (fecal calprotectin). This parameter will be summarized descriptively as a continuous parameter and results (including changes from baseline) presented by visit.
- Qualitative microbiology cultures: the presence of bacteria will be descriptively summarized by subject counts and percentages by visit. Shifts from baseline may be presented, as appropriate.
- Pulmonary exacerbations: Pulmonary exacerbations (PE_x) will be identified using the definitions provided in Section 11.5.3 of the protocol, and will be analyzed in 3 ways, as follows:
 - The number of pulmonary exacerbations will be normalized to an annual period to adjust for differences in time spent on study and summarized as a continuous variable using descriptive summary statistics.
 - The number of days with pulmonary exacerbations (cumulative duration) will be normalized to an annual period to adjust for differences in time spent on study and summarized as a continuous variable using descriptive summary statistics.

- The time-to-first pulmonary exacerbation in 96 weeks, total treatment duration will be analyzed using the Kaplan-Meier method (provided the number of subjects with events observed is adequate) and the event-free rate.
- Rate of CF-related hospitalizations will be analyzed in 3 ways, as follows:

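### TEAEs are planned only as crude percentages of the Safety Set, which will understate long-term (96-week) risk to the extent that subjects leave early

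*SAP*

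**What the plan says.** Safety is the primary endpoint (Protocol 7.1.1), and Protocol 12.3.4 treats TEAEs as the main safety assessment. The objective concerns long-term treatment, with 96 weeks of planned dosing: "Ivacaftor will be administered every 12 hours (q12h) from Day 1 through the morning dose of the Week 96 Visit" (Protocol 9.1.1.2).

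SAP 8.4.1 tabulates TEAEs by system organ class and preferred term as the "number and percentage of subjects with an event", counting each subject once. SAP 8.4 uses the whole Safety Set of the ivacaftor arm. Protocol 12.3.4.1 also plans counts and percentages. Neither document plans a rate per patient-year, a Kaplan-Meier estimate or a cumulative incidence for TEAEs.

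Follow-up can be unequal:

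- Protocol 9.1.1.5 stops study dosing for subjects who take commercial ivacaftor.
- Protocol 9.7 also gives the sponsor discretion to take subjects off the study, under this condition: "During the course of the study, if ivacaftor is approved and available for the treatment of CF in populations enrolled in this study".
- Protocol 9.1.1.3 does not require the Safety Follow-up Visit for subjects who switch. Under SAP 8.1 the TE period of a subject without that visit ends 28 days after the last dose.
- Protocol 9.8 lets nonsafety withdrawals be replaced, which can add partly followed subjects to the denominator.

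For pulmonary exacerbations and CF-related hospitalizations, SAP 8.3.3.2 says that event counts and days "will be normalized to an annual period to adjust for differences in time spent on study". It also plans Kaplan-Meier for the first event of each, if there are enough events.

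**The concern.** The study's main product is a description of how often adverse events occur in very young children over about two years of treatment. A crude percentage gives a subject who leaves at Week 24 the same weight in the denominator as one followed to Week 96, though the first had a quarter of the time on treatment in which to show an event. The figure therefore depends on how many subjects leave and when, as well as on the drug and the disease.

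The loss is greatest for events that appear late, and these are a main reason to run a 96-week study. The SAP already applies the principle to two tertiary event endpoints in the same subjects. The safety tables offer no equivalent, so a reader could not tell a low percentage due to low risk from one due to short follow-up.

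**Working it through.** **What there is to reproduce.** Nothing numerical. The plan states no incidence, event count or power: "The study is not powered to detect a significant treatment effect", "The study will enroll approximately 75 subjects" and "No statistical hypothesis testing will be conducted". The arithmetic below illustrates size and is not a forecast.

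**Inputs from the documents.** Dosing lasts 96 weeks. There is one analysed arm: "all analyses will be done for subjects from the Ivacaftor Arm only". The TE tail is 28 days (4 weeks) after the last dose where there is no Safety Follow-up Visit. That visit is itself due at about 4 weeks, so 4 weeks is used for everyone.

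**Assumed inputs.** The documents give neither a leaving rate nor a TEAE rate. True 96-week risk R is set at 10%, 20% or 50%. The share leaving, f, is 20%, one third or 50%, all at week w = 24 or 48. The hazard is constant and continues through the tail, and leaving is unrelated to event risk.

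**Formulas.**

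- Hazard per week: λ = −ln(1 − R)/96
- Expected crude proportion: C = (1 − f)·[1 − exp(−100λ)] + f·[1 − exp(−λ(w + 4))]
- Relative shortfall: 1 − C/R

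**Worked case: R = 20%, f = 1/3, w = 24.**

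- λ = −ln(0.80)/96 = 0.002324
- Completers: 1 − exp(−0.2324) = 0.2074
- Leavers: 1 − exp(−28 × 0.002324) = 0.0630
- C = (2/3)(0.2074) + (1/3)(0.0630) = 0.1383 + 0.0210 = 0.159
- Shortfall: 1 − 0.159/0.20 = about 20%

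Ignoring the tail gives (2/3)(0.20) + (1/3)(0.0543) = 0.151, a shortfall of about 24%. The tail matters and should be counted.

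**Range over the grid, tail included.**

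| True 96-week risk | Leaving | Expected crude % | Relative shortfall |
|---|---|---|---|
| 50% | 20% at Week 48 | 47.4 | 5% |
| 20% | 20% at Week 48 | 18.9 | 6% |
| 20% | one third at Week 24 | 15.9 | 20% |
| 50% | one third at Week 24 | 40.4 | 19% |
| 20% | 50% at Week 24 | 13.5 | 32% |
| 10% | 50% at Week 24 | 6.7 | 33% |

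**Where it vanishes.** With 10% leaving at Week 48, a true 30% shows as 29.7% and a true 10% as 9.9%. With no leavers, a true 30% shows as 31.0%, slightly high because of the tail. Events that all occur before anyone leaves show no shortfall.

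**Where it is worst.** If a 20% risk arises wholly after Week 48 and 30% have already gone, the crude figure is 0.20 × 0.70 = 14% (tail ignored).

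**Does adjustment recover the risk?** A simulation used 75 subjects, 4,000 runs, a true 30%, leaving spread uniformly over 96 weeks and no tail. The crude percentage averaged 25.8% with 30% leaving and 22.9% with 50% leaving. 1-KM at Week 96 averaged 30.0% in both cases. The exposure-adjusted rate, converted to a 96-week risk, averaged 30.0% and 29.9%. The simulation has constant hazard and non-informative leaving built in.

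**The case against.** The case for leaving the plan alone has several sound parts.

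- **No leaving rate is given.** A reader might infer that the 96-week risk is understated as a matter of fact. The documents do not support that: the shortfall is conditional and may be negligible. The SAP also never calls its percentage a 96-week risk.
- **Switching is allowed, not expected.** Protocol 9.7 is conditional, and the later clarification reproduced in SAP 2.1 speaks of a subject choosing to switch.
- **The contrast within the SAP is narrow.** A reader might infer that every other event endpoint is time-adjusted. LFT and ECG threshold events (SAP 8.4.2 and 8.4.3) and cataract incidence (SAP 8.4.6) are also crude. The two annualised endpoints are efficacy endpoints defined as rates, so annualising them follows from their definition.
- **Unequal follow-up is partly visible.** Exposure duration, discontinuation reasons and last treatment visit are summarised (SAP 8.2.1 and 8.2.4), and all AEs are listed by subject.
- **One analysed arm** means no between-arm bias.
- **Rollover subjects are not newly exposed.** They bring treatment from Study 124, which patient-years in this study would not count.

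All of these narrow the point, but none removes it. Separate exposure tables show that follow-up differs without letting a reader adjust any particular AE percentage, and absolute long-term incidence is what this study reports.

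**Conclusion.** The point holds as a conditional one. The crude percentage will understate 96-week TEAE risk to the extent that subjects leave early, most for late-onset events. If 20% to 50% leave at Week 24 to 48, the relative shortfall is about 5% to 33%. This assumes a constant hazard, leaving unrelated to event risk and a 4-week tail. With few or late leavers, or early-onset events, it is near zero.

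The planned tables are valid descriptions of what was observed and follow the protocol, so this is a worthwhile addition to the plan and not the correction of an error. The stronger readings, that understatement is established or that the SAP adjusts every event endpoint except adverse events, go beyond the documents.

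**What to change.** Keep the crude tables and add to SAP 8.4.1 and 8.4.2:

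1. Total patient-years in the TE period, shown in the table header.
2. First-event rates per 100 patient-years for any, serious, related and discontinuation-leading TEAEs, and for LFT threshold elevations. Person-time runs from first dose to first event or the end of the TE period.
3. For key events, 1-KM or cumulative incidence at Week 96 where numbers allow. This answers the 96-week question without a constant-hazard assumption.

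Treat lens opacity separately in SAP 8.4.6. OEs are about 24 weeks apart (Protocol 11.6.5), so onset dates are known only to an interval. The Follow-up OE, 24 weeks after the last dose (Protocol 9.1.1.4), falls outside the TE period, so a TE-period rate would drop findings made there. Report cumulative incidence by scheduled OE, using the number examined at each as the denominator and including the Follow-up OE. Showing that number matters because SAP 2.1 waives the Follow-up OE for rollover subjects who start commercial ivacaftor.

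The cost is a few descriptive rows from dosing, AE and examination dates already collected, with no testing. A footnote should state that the rate assumes a roughly constant hazard and covers Study 126 exposure only, so rollover subjects' treatment in Study 124 is excluded.

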8.4.2 Clinical Laboratory

For treatment-emergent laboratory measurements, the raw values and change from baseline values of the continuous hematology and chemistry results will be summarized in SI units by visit.

For selected LFT parameters, the number and percentage of subjects meeting at least 1 threshold analysis criterion event, during the TE period, will be summarized. The threshold analysis criteria are provided in Appendix E.

In addition, a listing containing individual subject hematology and chemistry values outside the normal reference ranges will be provided. This listing will include data from both scheduled and unscheduled visits.

8.4.3 Electrocardiogram

For treatment-emergent ECG measurements, a summary of raw values and change from baseline values will be provided by visit for the following standard 12-lead ECG measurements: RR (ms), HR (bpm), PR (ms), QRS duration (ms), QRS axis (degrees), QT (ms), and QT corrected for HR intervals [QTcF (ms)].

The number and percentage of subjects meeting at least 1 threshold analysis criterion during the TE period for the Treatment Period will be summarized. The threshold analysis criteria are provided in Appendix E.

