#### **11.6.4 Electrocardiograms (Ivacaftor Arm Only)**

Standard 12-lead ECGs will be performed using a machine with printout. Additional standard 12-lead ECGs will be performed at any other time if clinically indicated. The performance of all ECGs will adhere to the following guidelines:

- The subject will rest in the supine position for at least 5 minutes, if possible, before having an ECG performed.
- The ECG will be performed predose through the Week 24 Visit before any other procedures that may affect heart rate, such as blood draws. Following the Week 24 Visit, ECGs may be taken pre- or post-dose.

The ECG traces will be manually read at the study site at the Screening Visit and Safety Follow-up Visit. A printout of the ECG traces will be made for safety review by the investigator and maintained with source documentation. Clinically significant ECG abnormalities occurring during the study through the Safety Follow-up Visit will be recorded as AEs.

Study sites should use QTcF unless they receive approval in advance from the Vertex medical monitor or authorized designee to use QTcB.

To ensure safety of the subjects, a qualified individual at the study site will make comparisons to baseline measurements. If the QTcF is increased by >60 msec from the baseline or an absolute QTcF value is  $\geq 500$  msec for any scheduled ECG, 2 additional ECGs will be performed approximately 2 to 4 minutes apart to confirm the original measurement. If either of the QTcF values from these repeated ECGs remains above the threshold value (>60 msec from baseline or  $\geq 500$  msec), a single ECG will be repeated at least hourly until QTcF values from 2 successive ECGs fall below the threshold value that triggered the repeat measurement. A subject with a QTcF value above the threshold value will discontinue dosing.

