#### **12.3.4.3 Electrocardiogram (Ivacaftor Arm Only)**

Continuous ECG measurements will be summarized by visit and treatment. Changes from baseline will also be summarized. In addition, the number and percentage of subjects by maximum and minimum on-treatment value and by maximum and minimum on-treatment increase from baseline in QTcF intervals will be presented.

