Appendix E: Criteria for Threshold Analysis

Table 11-6 Threshold Analysis Criteria for Laboratory Tests (as applicable)

Parameter	Threshold Analysis	Comments
Clinical Chemistry (LFT)		
ALT	\leq ULN >ULN - \leq 2xULN >2xULN - \leq 3xULN >3xULN - \leq 5xULN >5xULN- \leq 8xULN >8xULN	FDA DILI Guidance
AST	\leq ULN >ULN - \leq 2xULN >2xULN - \leq 3xULN >3xULN - \leq 5xULN >5xULN- \leq 8xULN >8xULN	FDA DILI Guidance
ALT or AST	\leq ULN >ULN - \leq 2xULN >2xULN - \leq 3xULN >3xULN - \leq 5xULN >5xULN- \leq 8xULN >8xULN	FDA DILI Guidance
Total Bilirubin	\leq ULN >ULN - \leq 2xULN >2xULN - \leq 3xULN >3xULN - \leq 5xULN >5xULN- \leq 8xULN >8xULN	FDA DILI Guidance
(ALT or AST) and Total Bilirubin	(ALT>3xULN or AST>3xULN) and TBILI>2xULN	FDA DILI Guidance

Table 11-7 Threshold Analysis Criteria for ECGs

Parameter	Threshold Analysis	Comments
QT interval corrected by Fridericia's formula	\leq 450 msec >450 to \leq 480 msec >480 to \leq 500 msec >500 msec

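### As readable, the SAP counts subjects only in absolute QTcF bands and omits, without declaring it, the protocol's count by largest QTcF rise from baseline

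*SAP*

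**What the plan says.** **Protocol.** Twelve-lead ECGs are part of the primary safety endpoint (7.1.1). Section 12.3.4.3 plans counts and percentages of subjects by extreme on-treatment QTcF value, and it adds that counts "by maximum and minimum on-treatment increase from baseline in QTcF intervals will be presented". It gives no cut-points. Section 11.6.4 defines an alert with two limbs. One is a change: "If the QTcF is increased by >60 msec from the baseline". The other is an absolute value of 500 msec or more. Either leads to repeat ECGs, and the section ends: "A subject with a QTcF value above the threshold value will discontinue dosing".

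**SAP.** Section 8.4.3 has two ECG outputs. The first is continuous: "a summary of raw values and change from baseline values will be provided by visit for the following standard 12-lead ECG measurements", with QTcF among those listed. The second is categorical: "The number and percentage of subjects meeting at least 1 threshold analysis criterion during the TE period for the Treatment Period will be summarized". The criteria are in Appendix E, Table 11-7 ("Threshold Analysis Criteria for ECGs"). As readable, that table has one parameter, QTcF, in four bands: up to 450, above 450 to 480, above 480 to 500, and above 500 msec. No row for change is visible.

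SAP 8.1 says that unscheduled records feed the derivation of largest and smallest change for safety analyses, but 8.4.3 names no ECG output that uses it. SAP 2.1 lists departures from the protocol. Its one ECG entry restores ECG visits missing from two schedule tables and says nothing about the count by rise.

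**The concern.** A large rise from a low starting value is what absolute bands cannot show, and it is the reason the protocol has a change limb in its alert and a planned count of changes. If the final tables count only absolute bands, a child who meets the change limb can sit in the same row as a child whose QTcF never moved. The study is open-label and descriptive, with about 75 subjects and safety as its primary endpoint. A safety count planned in the protocol should therefore either appear in the SAP or be declared as dropped.

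**Working it through.** There is no power or sample-size figure to reproduce here. The check compares the planned outputs and then classifies some values.

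**1. Outputs side by side**

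| QTcF output | Protocol 12.3.4.3 | SAP 8.4.3 and Table 11-7 |
|---|---|---|
| Continuous values and change, by visit | yes | yes |
| Subjects by extreme on-treatment value | yes | yes for high values (four absolute bands) |
| Subjects by extreme on-treatment rise from baseline | yes | none visible |
| Removal declared in SAP 2.1 | n/a | no |

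**2. Where a rise above 60 msec falls in the SAP bands**

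Inputs: the protocol's cut (more than 60 msec, so 61 in whole msec) and the SAP bands. Baselines are assumed for illustration. Formula: on-treatment QTcF = baseline + 61.

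| Assumed baseline (msec) | Baseline + 61 | SAP band |
|---|---|---|
| 340 | 401 | up to 450 |
| 360 | 421 | up to 450 |
| 380 | 441 | up to 450 |
| 389 | 450 | up to 450 |
| 390 | 451 | above 450 to 480 |
| 420 | 481 | above 480 to 500 |
| 440 | 501 | above 500 |

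Every row meets the protocol's change limb. The highest baseline that can do so within the lowest band is 450 − 61 = 389 msec. The largest rise that stays in that band is 450 − baseline: 110 msec from 340, 90 from 360 and 70 from 380.

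**3. Does the by-visit change summary fill the gap?**

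It reports a maximum at each visit (SAP 8.1), so a large rise in the selected record would be visible. Three things limit it.

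- It does not say how many subjects ever exceeded 60 msec. Visit maxima cannot be added up across visits, because the same child may supply several of them.
- SAP 8.1 keeps the record closest to the target day. The worst record is used only for the threshold analysis, which has absolute bands only. For rollover subjects, SAP 2.1 restores ECGs at Weeks 12, 36, 60 and 84, but Table 11-4 has ECG windows only for Weeks 24, 48, 72 and 96. The Week 24 window, days 2 to 252, contains target days 84, 168 and 252. A Week 12 ECG on its target day is 168 − 84 = 84 days from the Week 24 target, so an on-schedule Week 24 ECG displaces it. The same holds for Weeks 36, 60 and 84. Four of the eight scheduled on-treatment ECGs can thus drop out of the rollover change summary.
- When records are equally close to the target day, SAP 8.1 takes the latest. After an alert, protocol 11.6.4 continues repeat ECGs until values are back below the triggering threshold. If the repeats are entered as records and same-day ties are broken by clock time, the record selected for that day is one taken after the peak.

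**4. The 500 msec boundary**

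The protocol's absolute limb is 500 msec or more, while the SAP's top band is above 500. A value of exactly 500 meets the alert but falls in the band above 480 to 500. The absolute limb therefore cannot be counted exactly from Table 11-7 either.

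**5. What the missing count would show**

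One such child among 75 is 1/75 = 1.3% (exact 95% CI 0.03% to 7.2%).

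**The case against.** The strongest objection is that Table 11-7 is the last text in the file. Rows for change could follow its final visible band and have been lost when the PDF was read. Section 8.4.3 cannot settle this, because it sends all categorical ECG criteria to Appendix E. The 8.1 rule on deriving largest change also suggests that some such output was intended. This stands as a condition: the source table must be checked first. It does not show that rows were lost, and nothing readable names an ECG output using that derivation.

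The second objection is that other outputs can reveal such a child. These are the by-visit maximum change, the disposition table (a subject above the alert threshold stops dosing under protocol 11.6.4), adverse-event tables if the finding is recorded as an event, and subject listings. This also stands. A reader might infer that a rise above 60 msec would appear nowhere in the report, and the documents do not support that. None of these outputs is the per-subject QTcF count the protocol planned, though, and the adverse-event route depends on what the investigator records.

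Third, the example baselines are assumed. They show what the bands cannot separate, not how many children are affected.

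**Conclusion.** On the readable text, the protocol's count of subjects by largest QTcF rise is missing from the SAP and its removal is not declared. The consequence is specific: any child with a baseline of 389 msec or less can meet the more-than-60-msec limb and be counted only in the lowest band. The number of such children cannot be estimated, because the documents give no baseline QTcF. The finding rests on Table 11-7 being complete as read.

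Two stronger readings do not hold. One is that the SAP would report such a child as normal; it attaches no such label to the band up to 450 msec, which is simply the lowest. The other is that the sponsor deliberately dropped the analysis; the 8.1 derivation rule fits an oversight equally well.

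The point is worth acting on because ECG belongs to the primary safety endpoint and the repair is small. It is a gap in reporting. It does not call the protocol's alert into question.

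**What to change.** Check the end of Table 11-7 against the source SAP. If there are no change rows:

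1. In SAP 8.4.3 and Table 11-7, add the number and percentage of subjects by largest on-treatment QTcF rise from baseline in the treatment-emergent period, including unscheduled and repeat records. Include a category above 60 msec, taken from protocol 11.6.4. Any lower cut is optional, since the protocol names none.
2. State which baseline applies to rollover subjects. SAP 8.1 and Table 11-4 point to the Study 124 baseline. Protocol 12.3.1 also defines a Study 126 baseline and uses only that one for gap-transition subjects. The same child can fall in different rise categories under the two.
3. Reconcile the SAP's band above 500 msec with the protocol's limb of 500 msec or more, so that subjects meeting either limb can be counted.

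If the sponsor prefers to leave the count out, SAP 2.1 should say so and give the reason.

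The cost is a few lines of SAP text and one table block from ECG data already collected. No change to the clinical alert or the stopping rule is proposed.
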